11.3.5.3 Adenomyosis

The number and percentage of subjects with presence of adenomyosis will be summarized for each analysis group at Baseline and each relevant post-baseline visit in the Treatment and Post-Treatment Follow-up Periods. Analyses above will be conducted separately for results obtained from TAU/TVU and MRI.

For subjects initially randomized to placebo in the pivotal studies, baseline presence of adenomyosis is defined by considering available TAU/TVU or MRI results at Baseline of this extension study (prior to or on Study Day 14). If a subject has adenomyosis results only from either TAU/TVU or an MRI at Baseline, then the Baseline adenomyosis is determined by that result; if a subject has adenomyosis results from both TAU/TVU and MRI at Baseline and they differ, then the MRI adenomyosis result is used. If a subject has multiple assessments of the same type (TAU/TVU, MRI), the results closest and prior to Study Day 1 will be used.

Additionally, the subset of subjects with adenomyosis identified at any point during the Baseline or Treatment Period in the pivotal studies and extension study will be defined as follows. If a subject has adenomyosis identified via TAU/TVU or MRI at any time during the Baseline or Treatment Period in the pivotal studies and extension study, the subject will be included in this set. This will include subjects who have differing results during the Treatment Period. Post-Treatment results will not be considered in the definition of this subset.

11.3.5.4 Post-Treatment Menses

The time to first post-treatment menses is defined as the number of days between the last dose date of study drug and the first day of a subject's first post-treatment menses in the Post-Treatment Follow-up Period of the extension study. Menses are defined as having at least 1 day when uterine bleeding categories of bleeding and/or spotting were reported.

Truncated on-treatment menses at the last dose date, i.e., menses that are ongoing at the last dose date will be excluded, and the next occurrence of menses in the Post-Treatment Follow-up Period will be considered as the first post-treatment menses and will be used for reporting the time to first post-treatment menses. If the gap between two consecutive post-treatment menstrual cycles (or between truncated on-treatment menstrual cycle and the next post-treatment menstrual cycle) is 1 day apart or less (i.e., out of the two consecutive cycles, the start date of the second cycle – the end date of the first cycle ≤ 2), these two menstrual cycles will be combined as one menstrual cycle in determining the first post-treatment menses.

AH data will be used for post-treatment menses. If post-treatment menses could not be identified from available AH data, UBQ will be used. For the first UBQ that indicates bleeding ("Subject only has spotting that did not require the use of sanitary products" or "There was no visible blood on the sanitary products" not allowed) after the last dose date, the date of that UBQ will be considered as the first day of the subject's first post-treatment menses.

Volume of bleeding in a subject's first post-treatment menses will be calculated and summarized. Only AH data will be used for volume of bleeding in first post-treatment menses. Time to first post-treatment menses and volume of bleeding in first post-treatment menses will be summarized and analyzed separately for the following groups of subjects:

- All subjects who entered the Post-Treatment Follow-up Period of extension study.
- Subjects who entered the Post-Treatment Follow-up Period and were amenorrhiec at the Final Month in the Treatment Period of extension study. Amenorrhea is defined as in Section 11.3.2.
- Subjects who entered the Post-Treatment Follow-up Period and achieved suppression of bleeding at the Final Month in the Treatment Period of extension study. Suppression of bleeding is defined as in Section 11.3.3.

Based on the time to first post-treatment menses during the Post-Treatment Follow-up Period, each subject will be categorized into one of the following non-overlapping categories: Study End Days 1 – 28, Study End Days 29 – 56, Study End Days 57 – 84, Study End Days 85 – 112, Study End Days 113 – 140, Study End Days 141 – 168, and Study End Days \geq 168. Summary tables will present the number and percentage of subjects in the specified categories.

11.3.6 **Quality of Life Questionnaire**

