### **Post-Treatment Follow-Up Period**

During the 12-Month Post-Treatment Follow-Up Period, visits will occur either by phone or on-site from Months 1 through 12.

During the Phone Visits (Post-Treatment Follow-up Visits Month 2, Month 4, Month 5, Month 7, Month 8, Month 10 and Month 11), Site Personnel will discuss adverse events, concomitant medications, if applicable, obtain the results of the subject's self-administered urine pregnancy test and will remind subjects of the importance of consistent use of appropriate and effective dual non-hormonal contraception throughout the Post-Treatment Follow-Up Period. Subjects may begin taking hormonal contraceptive preparations only after completing the Post-Treatment Follow-Up Month 2 Visit and following the return to a full menses (menses with full menstrual flow) in the Post-Treatment Follow-Up Period. If the subject's full menses has not returned by the Post-Treatment Follow-Up Month 2 Visit, an adverse event of amenorrhea should be documented.

Subjects will be required to collect sanitary products for their first menses with full menstrual flow in the Post-Treatment Follow-Up Period. If the subject does not return sanitary products for her first full menses, she will be required to collect and return sanitary products for her next full menses. Subjects will return the sanitary products at a Product Collection Visit within approximately 5 days after cessation of bleeding or spotting. The Post-Treatment UBQ will be administered by Site Staff at each Phone or Site Visit until the subject has returned sanitary products from her first full menses in the Post-Treatment Follow-Up Period. Once a subject returns sanitary products from a full menses in the Post-Treatment Follow-Up Period, the Post-Treatment UBQ no longer needs to be completed.

All subjects will be required to have DXA scans at Post-Treatment Follow-Up Months 6 and 12.

Procedures and assessments in the Post-Treatment Follow-Up Period should be performed as specified in [Appendix C](#), Study Activities.

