#### **5.4.1 Discontinuation of Individual Subjects**

In the event that a subject withdraws or is prematurely discontinued from study drug treatment, the subject should complete the Treatment Period Premature Discontinuation Visit as soon as possible (preferably within 2 days of last dose of study drug, if possible) and undergo study procedures as outlined in [Appendix C](#), Study Activities. Subjects who prematurely discontinue during the Treatment Period are expected to enter the 12-Month Post-Treatment Follow-Up Period, unless discontinuing due to pregnancy. Each subsequent monthly Post-Treatment Follow-Up Period Visit should be scheduled based on the date of the last dose of study drug.

In the event that a subject withdraws or is prematurely discontinued during the Post-Treatment Follow-Up Period, the subject should complete the Post-Treatment Premature Discontinuation Visit as soon as possible and undergo study procedures as outlined in [Appendix C](#), Study Activities. These procedures should not interfere with the initiation of any new treatments or therapeutic modalities the Investigator determines are necessary to treat the subject's condition. The reason(s) for the discontinuation from the study will be recorded in the eCRFs.

All used and unused study drug containers will be returned to the study site.

If a subject becomes pregnant during the Treatment or Post-Treatment Follow-Up Periods, no additional study procedures, except an ultrasound will be conducted. Refer to Section 6.1.6 for instructions on reporting of a pregnancy to the Sponsor and the required follow-up on the subject/fetus and live births.

If a subject is discontinued from the study with an ongoing adverse event or an unresolved laboratory result that is clinically significant (as determined by the Investigator), the Investigator will attempt to provide follow-up until a satisfactory clinical resolution of the laboratory result or adverse event is achieved.

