**If yes, why were sanitary products not collected/returned? (Please select one response)**

- Subject only had spotting that did not require the use of sanitary products\*
- There was no visible blood on sanitary products\*
- Subject forgot to/did not collect\*
- Subject/Site discarded the sanitary products\*
- Subject is still bleeding/spotting; will return when bleeding/spotting complete
- Subject collected sanitary products and did not bring them in yet; will return sanitary products at a later date
- Other

\* Subject will be required to collect sanitary products for her next full menses.

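### The SAP rule for dating first post-treatment menses can report the second menses as the first, takes a questionnaire date as onset, and does not keep out on-treatment bleeding

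*SAP*

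**What the plan says.** SAP 11.3.5.4 defines the variable as "the number of days between the last dose date of study drug and the first day of a subject's first post-treatment menses". AH data come first: "If post-treatment menses could not be identified from available AH data, UBQ will be used". For the fallback, the SAP takes the first bleeding-positive UBQ (spotting-only and no-visible-blood answers do not qualify) and says that "the date of that UBQ will be considered as the first day of the subject's first post-treatment menses". The only protection against on-treatment bleeding in that section is that "menses that are ongoing at the last dose date will be excluded". Volume of the first menses comes from AH data alone, and times are tabulated in 28-day categories of Study End Days.

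The protocol governs what is collected. Under 5.1 (Post-Treatment Follow-Up Period), if a woman does not return products for her first full menses, "she will be required to collect and return sanitary products for her next full menses". Appendix E repeats this on the form for answers such as not having collected, or having discarded, the products: "Subject will be required to collect sanitary products for her next full menses". The Post-Treatment UBQ is given at every phone or site visit until products from a full menses are returned.

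Both UBQ forms ask about bleeding since the previous visit and record no bleeding date. Protocol 5.1 also has the Treatment Period UBQ given at the Premature Discontinuation Visit if no keg is returned. Protocol 5.4.1 places that visit "as soon as possible (preferably within 2 days of last dose of study drug, if possible", with no upper limit.

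**The concern.** Time to first post-treatment menses is a listed safety variable (protocol 5.3.5), and it is how the study describes the return of cycles after up to 12 months of suppression. The rule can misdate it in three ways.

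- **Missed first menses.** The protocol's recovery step, collecting the next menses, supplies AH data, and having AH data is exactly what stops the SAP from looking at the UBQ. The time is about one cycle too long, and the volume belongs to the wrong menses.
- **UBQ date as onset.** The bleeding began somewhere between the previous contact and the UBQ, so the UBQ date is an upper bound.
- **Look-back across the last dose.** A UBQ at the Premature Discontinuation Visit covers weeks on treatment. An undated yes cannot be tested against the exclusion of ongoing menses, and that exclusion does not address bleeding that ended before the last dose.

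Two safety outputs could also disagree. Under protocol 6.1.1.1, amenorrhea is an adverse event if menses has not returned by Follow-Up Month 2. A woman with an uncollected menses on Day 40, recorded by UBQ, has returned. With a 28-day cycle, the SAP would date her at Day 68.

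**Working it through.** The plan states no figure that depends on this rule, so there is none to reproduce. The check applies the rule to cases and then to an illustrative group.

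**Inputs from the documents.** A month is 28 days (protocol, Definition of Terms). Follow-up visit windows are ±7 days (protocol Table 1). SAP 7.4.2 counts data as post-treatment when obtained more than 3 days after the last dose, and UBQ is not among its exceptions. In Phase 2b Study M12-813 (protocol 3.2.2), among women amenorrheic on entering follow-up, 52% returned to menses at Month 1 and a further 42% at Month 2 in Cohort 1; the Cohort 2 figures are 59% and 38%.

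**Assumptions.** The share m of first menses not collected, with the next one collected, is 5%, 10% or 20%. Cycle length is 28 days (range 21 to 35). Return at Month 1 or Month 2 is read as Study End Days 1–28 or 29–56, and the remaining 6% return later.

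**Step 1: one missed menses.** True onset is Day 20, not collected, with a bleeding-positive UBQ on Day 28. The second menses begins on Day 20 + 28 = 48 (20 + 21 = 41 to 20 + 35 = 55). The SAP reports Day 48, category 29–56. The UBQ already shows return by Day 28, category 1–28.

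**Step 2: group illustration, Cohort 1.** Each missed onset moves one 28-day category later. Share in Days 1–28 = 52 × (1 − m). Share by Day 56 = 94 − 42 × m. Mean delay over all women = 28 × m.

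| m | Days 1–28 (from 52%) | By Day 56 (from 94%) | Mean delay |
|---|---|---|---|
| 5% | 49.4% | 91.9% | 1.4 days |
| 10% | 46.8% | 89.8% | 2.8 days |
| 20% | 41.6% | 85.6% | 5.6 days |

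For Cohort 2, the Days 1–28 share falls from 59% to 56.0%, 53.1% or 47.2%.

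**Step 3: UBQ date as onset.** With contacts on nominal days, the lag is 0 to 28 days, averaging 14 if onset is evenly spread over the interval. With one contact 7 days early and the next 7 days late, the lag can reach 28 + 7 + 7 = 42 days. A contact on Day 28 stays in category 1–28. A contact on Day 35 moves a Day 22 onset to category 29–56.

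**Step 4: Premature Discontinuation Visit.** Suppose no keg is returned, qualifying bleeding is reported since the last monthly visit, and AH later identifies no menses. If the UBQ is on Study End Day 2, SAP 11.3.5.4 alone gives 2 days, while the cut in 7.4.2 would exclude it. If the UBQ is on Day 5 or Day 14, it passes both rules and gives 5 or 14 days, although all the bleeding may have preceded the last dose.

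**The case against.** The strongest points on the other side are these.

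- **The three-day cut.** A reader might infer that the rule plainly produces false returns on Study End Days 1–3. The documents do not support that. SAP 7.4.1 and 7.4.2 place data from those days in the Treatment Period, and UBQ is not excepted. The case arises only if the wording of 11.3.5.4, after the last dose date, overrides 7.4.2. The SAP does not say which governs. Later Premature Discontinuation Visits remain a problem either way.
- **Completers.** A woman dosing up to her Month 6 Visit has that UBQ on the last dose date, not after it, and her next look-back starts there. This stands, so the third problem mainly concerns early discontinuation.
- **No self-contradiction.** The section excludes only menses ongoing at the last dose. Admitting bleeding that ended earlier is a gap, not a breach of its own exclusion.
- **Categories.** A reader might infer that every UBQ-dated woman is pushed into the next category. Step 3 shows otherwise: it takes a contact after the category boundary.
- **Frequency and consequence.** Products are collected on all bleeding days through the first full menses, which limits missed collections. SAP 12.1 plans no follow-up testing, and delayed return is also captured as an adverse event.
- **A charitable reading.** The fallback sentence could be taken to mean the first post-treatment menses, which would let the UBQ in. The SAP does not say so.

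A simple rule taking the earlier of AH and UBQ would also do harm. With previous contact on Day 0, AH onset on Day 26 and a still-bleeding UBQ on Day 28, an interval midpoint of Day 14 would replace a correct date.

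**Conclusion.** The concern holds in this bounded form. As written, the rule reports a collected second menses as the first when the first was wholly uncollected, in both date and volume. It treats an upper bound as an onset date, and it admits UBQs that look back into treatment. The last is clear for Premature Discontinuation Visits more than 3 days after the last dose, and conditional within 3 days.

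Only a descriptive safety variable is affected; the primary endpoint and sample size are not. The first two errors make return look later, and the third can make it look earlier.

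The table in the working is not an estimate of study bias. It rests on an assumed missed-collection rate, a 28-day cycle, and Phase 2b women who were all amenorrheic at follow-up entry, whereas the SAP also summarises everyone entering follow-up. The number of women who would be dated by UBQ is likewise unknown. The change is still worth making, because the rule is wrong for identifiable women and the data to correct it are already collected.

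**What to change.** Amend SAP 11.3.5.4 as follows.

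1. Use only UBQs whose look-back starts on or after the last dose date, and state how this fits with the three-day cut in 7.4.2.
2. Let an earlier bleeding-positive UBQ take precedence over a later AH-identified menses only when no AH data cover that look-back interval and the answer shows that products were not collected or were discarded. Answers that bleeding continues, or that products will be returned later, leave the AH date in place.
3. Treat UBQ-based onset as interval-censored between the previous contact and the UBQ date, and say how an interval spanning two reporting categories is tabulated.
4. Summarise first-menses volume only where the collected menses is the first.

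The cost is SAP wording and a small programming change. Visit dates, UBQ dates and UBQ answers are already recorded, and no study procedure changes. The downside is that some women get an interval instead of an exact day, and some drop out of the volume summary.

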11.3.6.1 Uterine Fibroid Symptoms Quality of Life (UFS-QoL)

Improvement in quality of life will be assessed on the UFS-QoL Questionnaire (4-week recall). The change from Baseline to Month 3, Month 6, and Final Visit during the Treatment Period will be calculated and summarized by analysis group for each of the UFS-QoL subscales (symptom severity, concern, activities, energy/mood, control, selfconscious, and sexual function) and the HRQL total. Missing scores will be dealt with using the methods recommended by the UFS-QoL Scoring Manual. The UFS-QoL questionnaire is presented in Appendix A, and the relevant UFS-QoL Scoring Manual is presented in Appendix B.

11.3.6.2 EQ-5D-5L

The EQ-5D-5L questions and relevant scoring rules are presented in Appendix E.

The number and percentage of subjects with answers in each category of the EQ-5D-5L (Mobility, Self-care, Usual activities, Pain/Discomfort, and Anxiety/Depression) domains will be summarized at Baseline, each planned assessment, and Final Visit during the Treatment Period by analysis group.

Subject's responses to the EQ-5D-5L will be combined into a unique health state using a 5-digit code with 1 digit from each of the 5 dimensions at Baseline, each planned assessment, and Final Visit during the Treatment Period. The EQ-5D-5L states will be converted into a single preference-weighted health utility index score by applying

Obvie Elagolix (ABT-620)

Elagolix (ABT-620) M12-816 – Statistical Analysis Plan Version 2.0 – 24 May 2018

country-specific weights if available or US weights if country-specific weights are unavailable.^{6,7}

The EQ VAS scale is numbered from 0 - 100, with 100 indicating the best health that a subject can imagine, and 0 indicating the worst health that a subject can imagine.

11.3.6.3 Patient Global Impression of Change (PGIC)

11.3.6.3.1 PGIC on Menstrual Bleeding Questionnaire

For PGIC on menstrual bleeding (PGIC – MB, Appendix C), the number and percentage of subjects in each response category will be summarized at Month 1, Month 3, Month 6, and Final Visit by analysis group.

For PGIC – MB, the response categories of "Very Much Improved" and "Much Improved" will be combined together. The remaining five categories of the PGIC scale will be combined and labeled "Otherwise." The number and percentage of subjects with response of (a) "Very Much Improved" or "Much Improved," and (b) "Otherwise" will be summarized at Month 1, Month 3, Month 6, and Final Visit by analysis group.

11.3.6.3.2 PGIC on Non-Bleeding Uterine Fibroid Symptoms Questionnaire

For each of the PGIC questions on non-bleeding uterine fibroids symptoms (PGIC – NBUFS, Appendix D), the number and percentage of subjects in each response category will be summarized at Month 1, Month 3, Month 6, and Final Visit by analysis group.

For each of the PGIC – NBUFS questions, the response categories of "Very Much Improved" and "Much Improved" will be combined together. The remaining five categories of the PGIC scale will be combined and labeled "Otherwise." The number and percentage of subjects with response of (a) "Very Much Improved" or "Much Improved," and (b) "Otherwise" will be summarized at Month 1, Month 3, Month 6, and Final Visit by analysis group.

11.3.6.4 Work Productivity and Activity Questionnaire: Uterine Fibroids (WPAI:UF)

For each of the measures as presented in the scoring guide Appendix I based on the data collected via the WPAI:UF, the change from Baseline to Month 6 and Final Visit during the Treatment Period will be summarized by analysis group. The WPAI:UF is presented in Appendix H, and the WPAI:UF scoring guide is presented in Appendix I.

11.3.6.5 Health Care Resource Utilization Questionnaire (HCRU)

HCRU data will be summarized as observed; missing data will not be imputed. HCRU data will be summarized by analysis group at Months 1 - 6 and Final Visit. Descriptive statistics will be presented for the total number of Non-Study Health Care Practitioner Visits, overall and by the type of facility subjects were seen at. The number and percentage of subjects will also be presented by the type of Non-Study Health Care Practitioner who administered care to the subject.

The number and percentage of subjects will be presented by the type of diagnostic or therapeutic procedures performed based on HCRU at Months 1 - 6 and Final Visit during the Treatment Period.

11.3.6.6 Number of Days in Hospital

Hospitalization related data will be summarized as observed; missing data will not be imputed. Hospitalization data will be summarized by analysis group in the Treatment Period based on the Adverse Events eCRF.

The number and percentage of subjects who were hospitalized or had prolonged hospitalization will be summarized by analysis group. If a subject was hospitalized or had prolonged hospitalization multiple times during the Treatment Period, she will be counted only once.

The number of hospitalizations will be summarized by analysis group. The number of days in hospital (i.e., discharge date - admission date + 1) will be summarized by analysis

group. Only hospitalizations with an admission date on or after the first dose date and within 30 days following the last dose date (i.e., first dose date \leq admission date \leq last dose date +30) are included in the analysis of the number of days in hospital. If discharge date or admission date is missing, then the hospitalization will be excluded from the analysis of the number of days in hospital.

11.4 Handling of Multiplicity

No multiplicity adjustment is needed since only summary statistics will be provided for the efficacy analysis.

Safety Analysis 12.0

12.1 **General Considerations**

Safety analyses will be carried out using the Safety Analysis Set, which includes all subjects who received at least one dose of study drug. Safety data will be summarized by actual treatment received. If a subject receives more than one type of study drug, safety data will be analyzed in the treatment group to which she was randomized to. All safety analyses will be based on observed data. For analyses of safety endpoints, subjects who are missing an evaluation will not be included in the analysis of that particular parameter/visit, unless otherwise specified.

For continuous variables, when the analyses of change and/or percent change from Baseline to post-baseline visit(s) are performed, the within-group change from Baseline to each relevant visit will be summarized by analysis group with the mean, SD (or SE), and 95% CIs. The between-group differences of the two elagoix dose groups with at least 12 month of total exposure to elagolix in the Treatment Period will be summarized with the mean, SE, 95% CIs, and P value when applicable. At each post-baseline visit, the Baseline mean and post-baseline visit mean will be calculated for all subjects with baseline and post-baseline value at that visit by analysis group.

For qualitative categorical variables, Fisher's exact test will be used to analyze betweengroup differences when applicable. Categorical data will be summarized by number and percentage of subjects by analysis group.

Pregnancies and outcomes will also be summarized by analysis group.

Statistical comparisons will be performed for BMD between the two elagoix dose groups with at least 12 month of total exposure to elagolix in the Treatment Period, as specified in Section 12.4.1. There will be no testing for other safety endpoints in the Treatment Period. There will be no testing for safety endpoints in the Post-Treatment Follow-up Period.

Information regarding corresponding statistical methods for analyses and any additional statistical measures required for a specific variable/endpoint will be specified in the relevant sections.

12.2 **Adverse Events**

